The brief intervention will screen for food insecurity by a dietitian asking 2 questions to the dietitian service user. A pre-developed 2 item validated screening tool that assesses for food insecurity will be used. It uses the first two questions from the 18 item U.S. Household Food Security Survey. The two-item screen was validated by Hager et al. (2010) who reported a sensitivity of 97% and specificity 83% for identifying an affirmative response for either question. The tool has been validated in U.S as a shorter more practical tool in clinical practice. This is what The American Academy of Paediatrics (2015) endorse.

Once the dietitian has asked the two questions they will use the screening flow chart to advise why food security is important for good health and the clinical outcomes of their dietetic treatment, and then recommend what can be done to help act on food insecurity if present. To do this the dietitian will use two resources as appropriate (BDA Food Fact Sheet, Eat Well Spend Less and resource list for local food aid support). If trained, a referral voucher to a local foodbank will also be completed if appropriate. The dietitian will record the actions they take on the data collection tool.

There may be cases where a dietetic service user is recruited to participate in the study, but the dietitian does not complete the intervention (the 2 screening questions). It is important that the dietetic service user is advised how to access these food aid support resources if the intervention is not completed as their expectations may be raised that they are going to receive this information and they are not fulfilled. The dietetic service user will be advised on the participant information sheet '*Should the dietitian at your appointment not ask you the questions about food insecurity but you would like resources about this, please ask the researcher in the waiting area or contact the lead researcher (contact details on page 3) for this information*'.

STEP 1 ASK: 'I am going to read you two statements that people have made about their food situation. For each statement, please tell me whether the statement was often true, sometimes true or never true for your household in the last 12 months.'

1. "We worried whether our food would run out before we got money to buy more." Was that often true, sometimes true, or never true for your household in the last 12 months?

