We need to consider the different learning styles of the dietitians. Some may learn better from reading the materials others may learn from discussing the materials with the lead researcher and others may learn better from observing the materials be delivered. Research suggests delivery of information from a blended learning approach is the best. The blended learning approach is hoped to overcome any concerns or queries the dietitian may have prior to delivering the intervention.

Fidelity checking

To examine the fidelity of the intervention, the brief intervention component of a proportion of consultations by each dietitian will be audio-recorded to ensure that the dietitian is correctly implementing the screening tool as per the training protocol (1 in 10 brief interventions will be audio recorded by each dietitian). Audio recording is less intrusive and more cost effective than

implementing video recording or observations. The aim is to produce the least invasive way of checking fidelity. We also do not want to make the participant to feel uncomfortable.

Population

Dietitian service users attending NHS dietitian led clinics in the Coventry locality.

Where possible we want to target the dietitian clinics that are ran in the most deprived areas of Coventry for example Foleshill and Hillfields. Coventry is the chosen setting for the intervention as this is where the first study for this PhD has taken place and Coventry has a good food aid support network for those in need. Coventry Foodbank is one of the largest foodbanks in England and is further developed than many UK foodbanks in relation to the additional services they provide. It has been identified as a pioneering foodbank centre that aims to educate, empower and advance the social circumstances of clients attending. This has arisen due to the high prevalence of poverty and food poverty in Coventry and the growing need for this community support service. Coventry is a marmot city.

Eligibility criteria for dietitian service user

Inclusion

- Attending dietitian clinic
- Is ≥ 18 years of age or their main care giver is ≥ 18 years of age
- Is willing and able to provide informed consent to participate and comply with the study procedures
- Is able to understand English

Exclusion

Individuals fulfilling one or more of the following criteria are not eligible to participate in the study:

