- The dietitian deems it inappropriate to make an opportunistic brief intervention on food insecurity. This includes personal and medical reasons known to the dietitian or reasons related to the consultation (for example the dietitian service user has become distressed and it would seem insensitive to complete the intervention at that time).
- Is <18 years of age and their main care giver is <18 years of age
- No interpreter present, therefore the potential participant is unable to understand and speak English sufficiently to give informed consent
- Lacks capacity to give informed consent.
- Has a diagnosed severe eating disorder

Sampling strategy

Dietetic service user: purposive sampling, all dietitian service users attending dietitian clinic where the dietitian is trained to deliver the brief intervention will be invited to participate in the research

Dietitian: purposive sampling, dietitians who undertake dietitian clinics will be invited to participate in the research

Sample size

A sample size has not been predicted as it is a feasibility study. The study needs enough time to test the process and ensure that food insecure individuals are attending clinic where the research is being tested.

It is anticipated to recruit 5 dietitians and attend 10 of their clinics. Each clinic on average has 5 people in it and a 20% DNA rate. This exposes potentially 200 potential recruits to the study.

Outcome measures

1. Feasibility is to be measured by the number of dietetic service users consenting to take part, the number of completed brief interventions and the number of dietetic service users identified with food insecurity.
2. Dietetic service user's acceptability will be measured by the percentage of those identified as food insecure acting on the advice provided. This will be assessed by a telephone call from the researcher to the dietetic service user 2 weeks post intervention. The dietetic service user will also be asked about their experience of the brief intervention during this call. The telephone call will take the nature of a semi structured interview and be audio recorded. Once the telephone call is completed this will be the end of the study for the patient. 2 weeks was selected as there is no current literature to suggest a different timeframe. Self-reporting is acknowledged as a weak design however it is the most feasible and practical way of obtaining the relevant information.

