3. Dietitian's acceptability of the intervention will be analysed quantitatively by the number of records of consented dietitian service users not screened. At the end of the study Dietitians will be invited to attend a focus group with other dietitians who completed the brief intervention for food insecurity to discuss the feasibility and acceptability of the brief intervention. Once the focus group has been completed this will be the end of the study for the Dietitian. A focus group is more time-efficient than completing one to one interviews and allows thoughts to be developed and shaped by peer-to-peer discussion, rather than a collection of single reflections

4. Consent and recruitment of participants

Dietitian service user

All dietitian services users attending dietitian clinics where the brief intervention is being tested will be invited to participate in the research. Recruitment of the dietitian service user will take place in the dietitian waiting area whilst they are waiting for their appointment. The potential participants will first be approached by the researcher in which a verbal explanation and a copy of the participant information sheet will be given. The dietetic service user will be provided with adequate time to consider their participation in the study. They will have time to read the participant information sheet and will have the opportunity to ask any questions they may have, in order to decide whether they wish to participate in the study or not. If the dietitian service user is willing to participate in the study, they will keep the participant information sheet and sign the consent form.

Dietitian

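### Outcome 3 pools dietitian exclusions made after consent with non-delivery, and the two language criteria leave interpreter users undecided

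*Combined protocol and SAP*

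**What the plan says.** **Consent, exclusion and outcome 3.** Section 4 of the protocol places consent before the consultation: "Recruitment of the dietitian service user will take place in the dietitian waiting area whilst they are waiting for their appointment". The first exclusion criterion in section 3 (Eligibility criteria) applies when "The dietitian deems it inappropriate to make an opportunistic brief intervention on food insecurity". It covers personal and medical reasons and also reasons that come up in the consultation. Its own example is that "the dietitian service user has become distressed and it would seem insensitive to complete the intervention at that time". Meeting any one exclusion criterion makes a person ineligible.

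Outcome 3 (section 3, Outcome measures) states that dietitian acceptability will be "analysed quantitatively by the number of records of consented dietitian service users not screened". It adds a focus group of dietitians at the end of the study. The Intervention subsection foresees unscreened participants: "There may be cases where a dietetic service user is recruited to participate in the study, but the dietitian does not complete the intervention". What it then arranges is that they can still obtain the food aid resources. It also says that the dietitian records the actions taken on a data collection tool. Section 5 allows withdrawal at any time, and lets data collected before withdrawal be used only if the participant has agreed to that. Section 7 plans descriptive percentages, among them percentage eligible and percentage screened, with no breakdown by reason.

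**Language.** Inclusion: "Is able to understand English". Exclusion: "No interpreter present, therefore the potential participant is unable to understand and speak English sufficiently to give informed consent". Outcome 2 depends on a call to the participant: "This will be assessed by a telephone call from the researcher to the dietetic service user 2 weeks post intervention".

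**The concern.** Outcome 3 is the only quantitative measure listed for dietitian acceptability, and acceptability is one of the study's aims. A dietitian who judges that a distressed person should not be asked the questions, as the exclusion criterion allows, adds one to the count. So does a dietitian who forgets, runs out of time or prefers not to ask. The reader of the results could not tell a cautious use of the eligibility rule from an intervention that dietitians do not deliver, and these call for different responses in any later study. Percentage screened, taken over consented users, inherits the same mix.

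The language criteria raise a smaller problem of who is in the study. Two researchers following the text could admit or refuse the same interpreter user, which would shift percentage eligible and the outcome 1 counts. If such people are admitted, outcome 2 depends on a telephone interview for which the visible text mentions no interpreter.

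**Working it through.** **Step 1: order of events.** Consent is signed in the waiting area. The consultation follows. The exclusion can be triggered in the consultation. A person can therefore be consented first and excluded afterwards. Someone excluded before consent never enters outcome 3, so the issue is confined to exclusions made after consent.

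**Step 2: what the count contains.** Write

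outcome 3 = j + w + d

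- j: exclusions by dietitian judgement after consent
- w: participants who withdrew before screening and agreed to use of their data
- d: participants to whom the dietitian did not deliver the questions

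Only the sum is defined. A reported count of 20, for example, is compatible with any d from 0 to 20. This needs no assumption about rates.

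**Step 3: the plan's own figure.** Section 3 (Sample size) gives 5 dietitians, 10 clinics, 5 people per clinic and 20% non-attendance:

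5 × 10 × 5 × (1 − 0.20) = 200

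This reproduces the stated 200 potential recruits, reading 10 clinics as 10 per dietitian (10 in total would give 10 × 5 × 0.80 = 40).

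**Step 4: illustration.** Every input here other than 200 is an assumption. Take C = 140 consenting of 200, and o = w + d = 10 unscreened for other reasons.

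| j | Outcome 3 = j + o | Share from j | Screened = C − j − o | Screened / C | Screened / (C − j) |
|---|---|---|---|---|---|
| 5 | 15 | 5/15 = 33.3% | 125 | 89.3% | 125/135 = 92.6% |
| 10 | 20 | 10/20 = 50.0% | 120 | 85.7% | 120/130 = 92.3% |
| 20 | 30 | 20/30 = 66.7% | 110 | 78.6% | 110/120 = 91.7% |

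Varying C at j = 20 and o = 10:

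- C = 100: 70/100 = 70.0% against 70/80 = 87.5%
- C = 160: 130/160 = 81.3% against 130/140 = 92.9%

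A second parameterisation uses rates, leaving withdrawals aside. Let a fraction e of consented users be excluded after consent, and a fraction s of the remainder be skipped. The unscreened share is e + (1 − e)s, and the part of it due to exclusion is e / [e + (1 − e)s]. With e and s each between 5% and 20%:

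- unscreened share: from 0.05 + 0.95 × 0.05 = 9.8% to 0.20 + 0.80 × 0.20 = 36.0%, against 5% to 20% among those still eligible
- part due to exclusion: from 0.05/0.24 = 20.8% to 0.20/0.24 = 83.3%

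**Step 5: language.** Take a service user who does not understand English and has an interpreter present. Inclusion read literally: not met. Exclusion read literally: not triggered, because it is conditional on no interpreter. The text contains no other mention of interpreters that would decide the case. If an assumed 5 to 20 attenders are in this position, they are 5/200 = 2.5% to 20/200 = 10% of attenders.

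**The case against.** The strongest reply is that the exclusion is discretionary. A dietitian who finds the questions too awkward or insensitive to ask may be showing exactly the reluctance that outcome 3 is meant to capture. This stands. A reader might infer that post-consent exclusions are pure contamination, forced by the protocol, and should be deleted from the count. The documents do not support that: ineligibility follows once the dietitian has judged, but the judgement is the dietitian's own. What remains is that the count does not separate the reasons.

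A reader might also infer that every distressed participant who withdraws inflates outcome 3. Section 5 does not support this either. Data collected before withdrawal may be used only with the participant's agreement, and that section ties distress mainly to being asked the two questions, so many such people would already have been at least partly screened.

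Next, this is a mixed-methods study, and the focus group will discuss barriers. That will help to interpret the count. But it is held at the end of the study and cannot assign a reason to each record. The data collection tool and the section 14 flow chart are not visible, so a reason field may exist and its absence cannot be asserted. Even if it exists, outcome 3 as defined and the percentages in section 7 pool all reasons.

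On language, the exclusion can be read as treating the interpreter as the means of understanding, which would admit interpreter users. Equally, all inclusion criteria must be met, which would shut them out and make the interpreter wording redundant. Both readings are reasonable, and that is the difficulty: neither is stated. A reader should not conclude that the plan settles the matter either way.

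**Conclusion.** The main point holds. As written, outcome 3 and percentage screened cannot distinguish dietitian-judgement exclusions made after consent from non-delivery, or from withdrawals before screening with agreed data use. This follows from the timing of consent, the wording of the first exclusion and the definition of the outcome, and needs no numerical assumption.

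Its size is unknown. The documents give no counts of exclusions, withdrawals or non-delivery, and the shares of 33% to 67% (or 21% to 83% under the other set of assumptions) only show that the mix could be large. A reader might take them as estimates of bias; they are not, since the ratio of assumed exclusions to assumed other reasons fixes the result. The analysis is descriptive and the visible text attaches no progression threshold to outcome 3, so what is at stake is interpretation. The change is worth making before data collection, because reasons not noted in clinic may not be recoverable later.

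The language conflict is secondary and largely a matter of drafting, but it leaves entry undecided for interpreter users.

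**What to change.** 1. For every consented service user not screened, record one reason: dietitian-judgement exclusion, participant withdrew, or dietitian did not deliver. If the data collection tool already has such a field, refer to it in outcome 3 and section 7.
2. Report post-consent exclusions on their own line between consented and screened.
3. Show outcome 3 and percentage screened both with and without those exclusions.
4. Reconcile the two language criteria into one rule of the sponsor's choosing, and make the arrangements for the 2-week telephone interview consistent with it.

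Cost: one field per unscreened record, one extra reporting line and a small wording change. The version without exclusions could flatter acceptability, because some exclusions may reflect reluctance; that is why both versions are shown. Depending on the language rule chosen, the further cost is either interpreter arrangements for the call or a narrower population.

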Recruitment of the dietitian will take place at the dietitian main department. A member of the research team will be invited to attend a department meeting to recruit. The potential participants will be introduced to the research using the participation information sheet and a verbal explanation given by the researcher. The dietitian will be provided with adequate time (with up to 24 hours) to consider their participation in the study. They will have time to read the participant information sheet and will be given an opportunity to ask any questions they may have in order to decide whether they wish to participate in the study or not. If the dietitian is willing to participate in the study, they will keep the participant information sheet and sign the consent form. They will also be provided with information on how to access the necessary training to complete the brief intervention for food insecurity.

5. Withdrawal

The participant can withdraw at any time from the study without giving a reason(s) and without their medical care or rights being affected. Data collected up to the point of withdrawal can only be used after withdrawal if the participant has consented to this.

As the dietetic service user will be asked two questions which may be considered sensitive, if the patient becomes distressed during the study they will be able to withdraw at any time, without giving a reason(s).

6. Duration

It is anticipated that the study period to gather all the necessary data will be 6 months. Study commencement July 2019. Recruitment of the dietitian to take place in July 2019. Data collection in Coventry clinics July 2019 – February 2020.

7. Analysis

Quantitative data analysis

Quantitative results will be reported using descriptive statistics, they will present the percentage of individual's eligible to take part, percentage consenting, percentage screened by the dietitian, percentage food insecure and percentage acting on advice. This data will be analysed using the statistical software package, IBM SPSS Statistics for Windows, Version 25.0 (2017).

Qualitative data analysis

A semi structured interview will be completed with the dietitian service user via telephone and a face to face focus group will be completed with the dietitians to assess the feasibility and acceptability of the implementation of the brief intervention in clinical practice, exploring the opportunities and barriers.

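### Consented service users who decline, stop or are not asked the screening questions have no date for the only follow-up call, so the service-user account is likely to rest mainly on those screened

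*Combined protocol and SAP*

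**What the plan says.** Section 3, Outcome measures, item 2 defines the service-user measure: "Dietetic service user's acceptability will be measured by the percentage of those identified as food insecure acting on the advice provided". It then gives the timing: "This will be assessed by a telephone call from the researcher to the dietetic service user 2 weeks post intervention". The same contact serves as the qualitative interview: "The dietetic service user will also be asked about their experience of the brief intervention during this call". It also closes participation: "Once the telephone call is completed this will be the end of the study for the patient". No other service-user follow-up is described.

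Section 3, Intervention recognises that some recruits will not be screened: "There may be cases where a dietetic service user is recruited to participate in the study, but the dietitian does not complete the intervention". For them the protocol says how to obtain the food-support resources. It says nothing about the call.

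Section 5 notes that the two questions may be sensitive and says that "if the patient becomes distressed during the study they will be able to withdraw at any time, without giving a reason(s". It adds: "Data collected up to the point of withdrawal can only be used after withdrawal if the participant has consented to this".

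Item 3 of the outcome measures uses the number of consented service users who were not screened as the quantitative measure of acceptability to dietitians.

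**The concern.** One of the two aims is to explore the experience of the brief intervention, including barriers, from the service user's side as well as the dietitian's. A person who consents and then would rather not answer, or answers one question and stops, has direct evidence of a barrier. The timing and the content of the only interview both presuppose that the intervention took place, so as written the plan gives these people no clear route to an interview.

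The quantitative measures do not fill the gap. The acceptability percentage needs a positive screen and advice to act on, so it cannot show whether being asked was acceptable. The count of consented people not screened does capture non-completion, but it is attributed to the dietitian whoever caused it. A refusal by the service user could therefore be missing from the service-user account and also be misread as reluctance by the dietitian.

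**Working it through.** **1. Routes by which a consented service user may not complete the questions**

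| Route | Where described | Initiated by | Call stated? |
|---|---|---|---|
| Dietitian does not complete the two questions | Section 3, Intervention | Dietitian | No; access to resources only |
| Dietitian judges the intervention inappropriate, with distress in the consultation as the example | Section 3, exclusion criteria | Dietitian | No; the person falls under the exclusion criteria |
| Distress, with withdrawal available | Section 5 | Service user | No; withdrawal is from the study |
| Declines or stops the questions but does not withdraw | Not described | Service user | Not stated |

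Withdrawal is the only exit described that the service user initiates. None of the four routes leads to a stated interview, and none supplies the date from which the two weeks run.

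**2. Order of events.** Consent is taken in the waiting area (Section 4), before the consultation in which the dietitian may invoke the exclusion criterion. A person who consented and then became distressed could be treated as a consented user not screened (item 3), as someone who meets an exclusion criterion, or as a withdrawal. The documents do not say which. Under the third reading, data already collected are usable only if the participant agreed to that.

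**3. Who enters each service-user measure**

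- Acceptability percentage: only people identified as food insecure. Screened food-secure users are outside it as well as unscreened users.
- Experience interview: the call population is not defined. The objective in Section 2 and the analysis in Section 7 refer to the service user in general terms.
- Consented but not screened: counted, but only under dietitian acceptability.

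**4. The plan's own figure.** Section 3, Sample size gives 200 potential recruits. Reading the ten clinics as ten per dietitian: 5 dietitians × 10 clinics × 5 people × (1 − 0.20) = 200. This reproduces. Ten clinics in total would give 10 × 5 × 0.80 = 40, which does not.

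**5. How many people might be affected.** The documents give no consent, screening or decline rate, so every rate below is assumed.

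- 60% consent: 200 × 0.60 = 120.
- 5% of these not screened: 120 × 0.05 = 6.
- 30% of these not screened: 120 × 0.30 = 36.
- Wider limits, with 30% to 90% consenting and 5% to 50% not screened: 200 × 0.30 × 0.05 = 3, up to 200 × 0.90 × 0.50 = 90.

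These counts mix people never asked with people who declined. The documents do not allow the two to be split.

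**6. What missing accounts could do.** Suppose a share d of consenters decline or stop and are not interviewed, and a share A of those interviewed find the intervention acceptable. The share among all consenters then lies between A(1 − d) and A(1 − d) + d. With A = 0.80 (assumed):

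- d = 0.05: 0.80 × 0.95 = 0.76, up to 0.76 + 0.05 = 0.81.
- d = 0.10: 0.72 to 0.82.
- d = 0.20: 0.64 to 0.84.
- d = 0.30: 0.56 to 0.86.

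The width of the interval equals d. These are limits and not an estimate of bias. The plan does not itself compute such a proportion from the interviews, so they show only how far an account drawn from screened people could differ from that of all consenters.

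**The case against.** A reader might infer that people who decline or stop are never interviewed. The documents do not say so. The stated timing says when the call is made, not who receives it. The interview objective and the analysis section do not limit it to completers, contact details are taken at consent (Section 11), and nothing bars a person who declines without withdrawing from being called. The flow chart in Section 14, the full information sheet and any interview guide are not in the text available, and any of them might define the call population. That objection stands: the gap is an undefined population with timing that points away from these people, not a rule excluding them.

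A reader might also infer that withdrawal is the only way out. That is too strong, because the protocol gives two dietitian-initiated routes. Nor does Section 5 say that declining a question amounts to leaving the study. It simply does not provide for the difference.

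Non-completion is not ignored either. Completed interventions, the percentage screened and consented users not screened are all reported, and the dietitian focus group could discuss refusals. Screened users can also voice objections in their interviews, and some who object may decline consent, which no change to the call would reach. All this is fair. What remains missing is the account of those who declined, in their own words, and a way to tell their refusal from the dietitian's decision.

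Finally, someone who was never asked has no experience of the questions to report. This is a reason to record who initiated non-completion, and not to treat every unscreened person as an objector.

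**Conclusion.** The concern holds in a limited form. The single service-user follow-up is anchored to an event that some consented people will not have, the plan does not say whether they are called, and stopping the questions is not separated from leaving the study. As written, the account of acceptability and barriers is likely to come mainly from people who were screened, the acceptability percentage comes only from those identified as food insecure, and a service user's refusal would be counted as dietitian non-acceptability.

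It would go too far to say that bias toward acceptability has been shown. Its size is unknown, and the counts in the working rest entirely on assumed rates. The conclusion also assumes that the parts of the documents not available do not already define who is called. The change is worth making because it bears directly on a stated aim and costs little.

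**What to change.** - In Outcome measures, item 2, time the call at two weeks after the clinic appointment, for every consented service user who has not withdrawn or refused further contact, whether or not screening was completed.
- In Section 5 and the information sheet, separate declining or stopping the questions, after which the call is still offered, from leaving the study, after which there is no contact.
- On the data collection tool, record whether the dietitian or the service user initiated non-completion, with any reason volunteered. In item 3, do not count service-user refusals as dietitian non-acceptability; report them separately.
- Reconcile this with the exclusion criterion that covers a person who becomes distressed in the consultation after consenting, so that it is clear how such a person is classified and whether the call applies.

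The cost is wording in a few places, one or two fields on an existing form, and some short extra calls by the researcher who already makes them, using contact details already held. On the assumptions shown (120 consenting, 5% to 30% not screened) that is about 6 to 36 calls. This is not an upper limit, since the wider assumed rates give 3 to 90. The right to withdraw without giving a reason is unchanged.
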